A Safety Run-in will be completed since there are no precedent data on the use of pembrolizumab with CRS-207. Subjects will be monitored for unacceptable toxicity during the first 28 days (through 7 days after the Cycle 2 dose). During the Safety Run-in evaluable subjects are defined as those who remain on study for the 28-day monitoring period, subjects with unacceptable toxicity, and subjects who are discontinued for safety reasons at the Investigator's discretion (even if criteria for unacceptable criteria are not met). Treatment of the first 6 subjects that are followed for the 28-day period will be staggered with no more than 1 subject treated per week. In the event that 4 in up to 12 safety-evaluable subjects experience an unacceptable toxicity, the subsequent cohort of 12 subjects enrolled will be administered CRS-207 at a dose reduced by a half-log (dose level -1). In the event of 4 subjects in up to the next 12 safety-evaluable subjects enrolled experience an unacceptable toxicity, the subsequent cohort of 12 subjects enrolled will be administered a reduced dose of CRS-207 (dose level -2). For each dose reduction (to a minimum of 1×10^8 CFU) the first 12 subjects will be treated and unacceptable toxicities assessed as described above. No adjustments will be made to the pembrolizumab dose.

Safety data and all unacceptable toxicities will be reviewed by a Safety Review Team (SRT) comprised of participating investigators in the study, the Medical Monitor, and Sponsor representatives. Once the Safety Run-in is complete, safety will continue to be evaluated on an ongoing basis in this open-label study. Cumulative clinical experience with CRS-207 and pembrolizumab will be used to assess whether AEs are considered expected.

The Schedule of Events is provided in [Table 1-1](#). Subjects who experience tolerability issues with same-day dosing may continue to follow the consecutive-day dosing regimen as in Cycle 1 with Day 1 pembrolizumab followed by Day 2 CRS-207 dosing ([Table 1-2](#)).

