Evaluable Analysis Set (EAS) is defined as all subjects who received at least 1 dose of CRS-207 and have at least one evaluable post-baseline RECIST tumor response assessment or were discontinued due to toxicity. The EAS will be the primary analysis set for the analyses of tumor-related endpoints (ORR, DCR, DOR, and PFS).

AE data will be coded to system organ class and preferred term using Medical Dictionary for Regulatory Activities (MedDRA; Version 18.1, or later). The number and percentage of subjects experiencing any TEAE, overall, and by system organ class and preferred term will be tabulated. The incidence rates adjusted by cumulative exposure will also be presented overall and by cycle. AEs associated with clinical laboratory parameters will be characterized according to NCI CTCAE, Version 4.03. Shifts in toxicity grades from baseline to each visit will be summarized.

Disease responses as determined by RECIST will be summarized by response level at each visit and best overall response. The ORR and DCR, along with a 95% CI will be summarized. PFS, DOR, and OS will be summarized using Kaplan-Meier methods.

SAMPLE SIZE DETERMINATION

This study is descriptive in nature, as such the sample size for this study is determined by practical rather than statistical considerations. Approximately 79 subjects will be enrolled with evaluable post-baseline tumor data. With 79 subjects, the precision for point estimate for ORR is as follows: the 95% CI width for ORR based on Wilson score intervals are at most the observed proportion +/- 0.108. If the observed ORR = 30.4% (24 of 79 subjects with PR or CR), the lower bound of the 95% CI would be 19.5%.

Table 1-1 Schedule of Events: Same-day (D1) Dosing Regimen

Study Phase	Screen	Cycle 1 [1]				Cycle 2 [1]				Cycle 3 [1]			Cycle 4 [1]		Cycle 5 and all future odd numbered cycles [1]		Cycle 6 and all future even numbered cycles [1]		EOT [2]	Follow-up	
Study Day	-28 to -1	1	2	3	7	1	2	7	15	1	2	7	1	7	1	1	1	1	±7		
Visit Window (days)	-	-	-	-	±1	±3	±1	±1	-7	±3	±1	±1	±3	±1	±3	±3	±3	±3			
Study Procedures																					
Informed Consent	X																				
Inclusion/Exclusion Criteria	X	X																			
Medical History, Height	X																				
Archived Tumor Specimen [3]	X																				
Tumor Biopsy [4]	X									X											
CT Tumor Evaluation [5]	X										X						X		X		
Survival, additional treatment [6]																				X	
ECOG Performance Status	X	X				X				X			X		X		X		X	X	

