6.5.1 Sample Size Determination

This study is descriptive in nature, as such the sample size for this study is determined by practical rather than statistical considerations. Approximately 79 subjects will be enrolled to achieve at least 79 treated subjects with evaluable post-baseline tumor data. With 79 subjects, the precision for point estimate for ORR is as follows: the 95% confidence interval (CI) width for ORR based on Wilson score intervals are at most the observed proportion +/- 0.108. If the

observed ORR = 30.4% (24 of 79 subjects with PR or CR), the lower bound of the 95% CI would be 19.5%.

Of the 79 subjects enrolled, an estimated 50 subjects will be enrolled with gastric or GEJ cancer, and an estimated 29 subjects will be enrolled with esophageal cancer. Assuming at least 50 evaluable gastric/GEJ subjects are evaluable for ORR, the precision for point estimate for ORR is as follows: the 95% CI width for ORR based on Wilson score intervals are at most the observed proportion +/- 0.134. Assuming at least 29 evaluable esophageal cancer subjects are evaluable for ORR, the precision for point estimate for ORR is as follows: the 95% CI width for ORR based on Wilson score intervals are at most the observed proportion +/- 0.173.

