6.5.2 General Considerations

The descriptive summary for the categorical variables will include counts and percentages. The descriptive summary for the continuous variables will include means, medians, standard deviations, Q1, Q3, and minimum and maximum values. The descriptive summaries of time to event data will include median, 25th and 75th percentiles, and standard error. All data will be listed for all subjects.

This study is descriptive in nature; no formal hypothesis testing will be performed. All CIs will be 95%, unless stated otherwise.

All statistical analyses will be performed using SAS.

The effects of noncompliance, dropouts, and covariates will be assessed to determine the impact on the general applicability of results from this study.

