4.1. Stratification and Covariates

There are no formal plans for analysis stratification.

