4.2. Evaluation of Subgroups

Subgroup analyses are not planned to be performed for the final analysis.

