10. SAFETY

All safety analysis reporting will be based on the SAF.

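### If the run-in lowers the CRS-207 dose, the Protocol's ORR and every SAP safety table mix dose levels, and no breakdown by dose is planned

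*Protocol*

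**What the plan says.** **Dose rule.** Under the Safety Run-in (Protocol Synopsis, 6.1 and 6.3.1; repeated in SAP 3.1), once 4 of up to 12 safety-evaluable subjects have an unacceptable toxicity, "the subsequent cohort of 12 subjects enrolled will be administered CRS-207 at a dose reduced by a half-log (dose level -1"). The same rule can apply again at the lower level. Protocol Table 6-3 lists the three levels: 1×10^9, 3×10^8 and 1×10^8 CFU. Pembrolizumab stays at 200 mg.

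**Protocol analysis.** "The EAS will be the primary analysis set for the analyses of tumor-related endpoints (ORR, DCR, DOR, and PFS"). Membership of the EAS and FAS requires at least one CRS-207 dose and membership of the SAF any study treatment; none of the three depends on dose level (6.5.4). Section 6.5.5.1 reports a single ORR in the EAS with a Wilson interval. Section 6.5.1 says "Approximately 79 subjects will be enrolled to achieve at least 79 treated subjects with evaluable post-baseline tumor data" and that "the 95% confidence interval (CI) width for ORR based on Wilson score intervals are at most the observed proportion +/- 0.108". It does not mention dose level.

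**SAP analysis.** "There are no formal plans for analysis stratification" (4.1). "Subgroup analyses are not planned to be performed for the final analysis" (4.2). "All safety analysis reporting will be based on the SAF" (10). SAP 5.1 treats all subjects as one combination group, SAP 6.1 uses the SAF alone, and no table title in 13.1 refers to dose level. SAP 7, 7.1, 7.2 and 11 have efficacy listed by subject and not summarized.

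**The concern.** A reduction is triggered by toxicity at the current dose, so the cohort left behind has, by construction, at least 4 unacceptable toxicities in at most 12 evaluable subjects. Pooling carries that cohort into every rate reported for the trial. The pooled rate then sits between the rates of the two regimens: too high for one of them, too low for the other, and not an estimate for either. The same holds for the Protocol's ORR if response differs by dose.

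Safety is the first objective in Protocol section 5, and safety is what the SAP still tabulates. Section 6.1.1 of the Protocol gives the trial's purpose as looking for initial safety and efficacy signals ahead of a larger randomized study, and such signals need to be tied to a dose.

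**Working it through.** **Inputs.** Trigger of 4 in up to 12, and levels of 1×10^9, 3×10^8 and 1×10^8 CFU (Protocol 6.3.1, Table 6-3). N = 79 and a maximum half-width of 0.108 (6.5.1). Confidence level: "All CIs will be 95%, unless stated otherwise" (6.5.2), so z = 1.96. True toxicity rates are not given and are assumed.

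**1. The plan's own figure.** The Wilson half-width is z·√(p(1−p)/n + z²/(4n²)) / (1 + z²/n). It is largest at p = 0.5, where it reduces to z / (2√(n + z²)). For n = 79: 1.96 / (2√82.84) = 0.1077, which reproduces the stated 0.108.

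**2. Chance of a reduction.** Reaching 4 toxicities within 12 subjects is the event X ≥ 4 with X ~ Binomial(12, p). For p = 0.20, P(X ≤ 3) = 0.0687 + 0.2062 + 0.2835 + 0.2362 = 0.7946, so the chance is 20.5%.

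| Assumed true rate | First 12 trigger | Both cohorts trigger, same rate at both doses |
|---|---|---|
| 10% | 2.6% | 0.07% |
| 20% | 20.5% | 4.2% |
| 30% | 50.7% | 25.8% |
| 40% | 77.5% | 60.0% |

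**3. Subjects at the retained dose.** The trigger can be met after as few as 4 subjects or as many as 12. Assume 79 evaluable subjects in total, no overrun at a dose once its trigger is met, and all later subjects kept at the reduced dose. One reduction leaves 79 − 12 = 67 to 79 − 4 = 75. Two leave 79 − 24 = 55 to 79 − 8 = 71.

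**4. Precision at the retained dose**, using the same formula at p = 0.5:

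| Case | n | Maximum half-width |
|---|---|---|
| No reduction | 79 | 0.108 |
| One reduction | 75 to 67 | 0.110 to 0.116 |
| Two reductions | 71 to 55 | 0.113 to 0.128 |

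A rejected-dose cohort of 12 has a maximum half-width of 0.246, and one of 4 has 0.350.

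**5. Size of the mixing (assumed rates, for illustration only).** Suppose a tabulated adverse event has a rate of 40% at the rejected dose and 15% at the retained dose.
- Split 12 and 67: (12×0.40 + 67×0.15)/79 = 14.85/79 = 18.8%.
- Split 4 and 75: (4×0.40 + 75×0.15)/79 = 12.85/79 = 16.3%.

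For ORR, assume 30.4% at the rejected dose and 20% at the retained dose: (12×0.304 + 67×0.20)/79 = 17.05/79 = 21.6%.

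After one reduction the retained dose carries 67/79 = 85% to 75/79 = 95% of the weight. The pooled figure therefore lies close to the retained-dose rate, and what the rejected dose showed is almost hidden.

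**The case against.** The strongest reply is that the trial is descriptive, has no hypothesis test, and handles run-in toxicity cohort by cohort through the Safety Review Team. The exposure table counts dose reductions (SAP 6.8), and CRS-207 administration and adverse events are listed by subject (SAP 13.2), so a split can be recovered. The Protocol calls its statistical section a guide (6.5) and allows further analysis sets (6.5.4).

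Much of this stands, but it does not remove the gap. A split from listings would be unplanned, and the pooled safety tables would remain the reported result. SAP 6.8 does not say whether a subject who starts at a lower level counts as a dose reduction. CRS-207 is summarized by duration, number of infusions and volume, never by CFU received. SAP 10.1 justifies its exposure-adjusted rate by differences between treatment categories but defines no such categories.

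Several stronger readings are tempting and are not supported:
- **That the study report will give a pooled ORR.** SAP 7, 7.1 and 11 rule out any efficacy summary. The ORR point applies to the Protocol's plan.
- **That a reduction took place.** Neither document says so.
- **That the stated precision collapses.** The like-for-like change is the one in step 4. The figures of 67 and 55 are minimums under the assumptions of step 3, not ceilings.
- **That a trigger proves the dose too toxic.** At a true rate of 20%, below the 4/12 threshold, it still fires 20.5% of the time.
- **That a later trial will rest on these figures.** SAP 3.5 records that the sponsor ceased CRS-207 development in December 2017.

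**Conclusion.** The point holds as a conditional one. The documents allow a tenfold range of CRS-207 dose, fix analysis sets that ignore dose, and plan no display by dose. If a run-in reduction occurs, the Protocol's ORR and all SAP safety tables combine a rejected and a retained regimen and describe neither. If none occurs, no result changes.

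The chance of a first reduction runs from 20.5% to 77.5% over assumed true rates of 20% to 40%. The defect is the mixing of regimens; the loss of precision at the retained dose is modest and depends on the assumptions in step 3. For safety the gap is in both documents; for ORR it is in the Protocol only.

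The SAP is dated 13 March 2018, and its section 3.5 says every subject had completed the end-of-treatment visit by 31 January 2018. Whether a reduction had happened could therefore have been stated, but the SAP repeats the rule and leaves the question open.

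**What to change.** **Protocol 6.5.4 to 6.5.6.** Add that, if a run-in reduction occurs, the ORR, DCR, TEAE, infusion-reaction and exposure tables have one column per assigned CRS-207 starting dose level plus a total, and that the ORR at the dose carried forward is the main one. Using the assigned starting level keeps the later individual dose changes allowed in 6.3.4.3 from moving subjects between columns.

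**SAP 4.1/4.2, 6.8 and 10.** State whether a run-in reduction occurred. If it did, present the safety and exposure tables by assigned starting dose level plus a total. If it did not, one sentence closes the point. Precision figures for 67 and 55 subjects need not be added to SAP 3.3, because treatment had ended and the SAP summarizes no ORR.

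**Cost.** Extra table columns, and a main Protocol ORR that rests on somewhat fewer subjects. Columns for a rejected dose may hold only 4 to 12 subjects and should be read as description.

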3 LIST OF ABBREVIATIONS AND DEFINITION OF TERMS

Abbreviation	Definition
AE	Adverse event
AESI	Adverse event of special interest
ALC	Absolute lymphocyte count
ANC	Absolute neutrophil count
ALT	Alanine aminotransferase
aPTT	Activated partial thromboplastin time
AST	Aspartate aminotransferase
CA19-9	Cancer antigen 19-9
CEA	Carcinoembryonic antigen
CFR	Code of Federal Regulations
CFU	Colony-forming units
CI	Confidence interval
CR	Complete response
CRA	Clinical research associate
CT	Computed tomography
CTCAE	Common Terminology Criteria For Adverse Events
DCR	Disease control rate
DOOR	Duration of response
EAS	Evaluable analysis set
EBV	Epstein-Barr virus
EC	Ethics committee
ECG	Electrocardiogram
ECI	Event of clinical interest
ECOG	Eastern Cooperative Oncology Group
eCRF	Electronic case report form
EDC	Electronic data capture
ELISA	Enzyme-linked immunosorbent assay
ELISPOT	enzyme-linked immunospot
EOT	End of Treatment
EU	European Union
FAS	Full analysis set
FDA	United States Food and Drug Administration
FT3	free triiodothyronine
FT4	free thyroxine
GCP	Good Clinical Practice
G-CSF	Granulocyte colony-stimulating factor
GEJ	gastroesophageal junction
GM-CSF	Granulocyte-macrophage colony-stimulating factor

Abbreviation	Definition
GVAX pancreas	Irradiated, whole-cell, allogeneic tumor immunotherapy
HIV	Human immunodeficiency virus
HLA	Human leukocyte antigen
IB	Investigator's Brochure
ICF	Informed consent form
ICH	International Conference on Harmonisation
IHC	Immunohistochemistry
INR	International normalized ratio of prothrombin time
IRB	Institutional Review Board
irAE	Immune-related adverse event
irRECIST	immune-related RECIST
IV	Intravenous
LADD	Live, attenuated, double-deleted
Lm	Listeria monocytogenes
MedDRA	Medical Dictionary for Regulatory Activities
MHC	Major histocompatibility complex
mOS	Median overall survival
MRI	Magnetic resonance imaging
MSI	Microsatellite instability
MTD	Maximum tolerated dose
NCI	National Cancer Institute
NSCLC	non-small cell lung carcinoma
ORR	Objective response rate
OS	Overall survival
PBMC	Peripheral blood mononuclear cells
PD-1	programmed death receptor-1
PD-L1	programmed death receptor ligand 1
PFS	Progression-free survival
PR	Partial response
PT	Prothrombin time
██████████	██████████
Q3W	Once every 3 weeks
Q6W	Once every 6 weeks
RECIST	Response evaluation criteria in solid tumors
SAE	Serious adverse event
SAP	Statistical Analysis Plan
SRT	Safety review team
T3	Triiodothyronine
TIL	Tumor infiltrating lymphocytes
TCR	T cell receptor

Abbreviation	Definition
TSH	thyroid stimulating hormone
ULN	Upper limit of normal
VEGF	Vascular endothelial growth factor
WBC	White blood cell

4 INTRODUCTION

In 2015, the National Cancer Institute estimated 16,980 new diagnoses of esophageal cancer and 24,590 new diagnoses of gastric cancer will occur in the United States (US). Together these cancers account for approximately 3% of all new cancer cases. Overall 5-year survival rates are approximately 20% for esophageal cancer and 30% for gastric cancer; approximately 50% of patients present with unresectable or locally advanced disease at the time of diagnosis ([NIH, 2015](#)).

Gastric cancer remains the fourth commonest diagnosed cancer and is the second leading cause of cancer-related death ([Jemal, 2011](#)). Patients with gastric cancer typically present with advanced disease. More than 50% of patients undergo surgical resection; however, the majority of them relapse locally or with distant metastases.

With new diagnoses in more than 480,000 patients annually, esophageal cancer is the eighth most common cancer worldwide ([Siegel, 2015](#)). It is a highly lethal disease, causing more than 400,000 deaths per year ([Ferlay, 2010](#)). The incidence of esophageal adenocarcinoma is rapidly rising, whereas that of squamous-cell carcinoma remains unchanged ([Parkin, 2001](#)). Despite adequate preoperative staging, 25% of patients treated with primary surgery have microscopically positive resection margins (R1) and the 5-year survival rate rarely exceeds 40% ([Devesa, 1998](#)).

Numerous advances have been made in the management and understanding of gastric and esophageal cancer, including improvements in diagnosis, histologic classification, and molecular biology. Despite these advances, patients with gastric and esophageal cancer have a poor prognosis and there is a clear unmet medical need for new treatment. New therapeutic strategies such as immunotherapy are under investigation.

Several lines of evidence suggest gastroesophageal cancers are good targets for immunotherapy (reviewed in [Wang, 2016](#)). An association between tumor infiltrating lymphocytes (TIL) and survival was first proposed over 100 years ago. Since then numerous studies have shown an increased density of TILs (including intratumoral B cells and NK cells) is associated with favorable clinical outcomes in gastric and esophageal cancer. In particular, the Epstein-Barr virus (EBV) and Microsatellite Instability (MSI) subtypes have been shown to have significant immune signatures including increased density of TILs. MSI cancers are also characterized by increased mutational load and presentation of neo-antigens. With the significant clinical benefits from immune checkpoint blockade drugs, novel opportunities are emerging for immunotherapy of gastric and esophageal cancers.

4.1 CRS-207 Immunotherapy

4.1.1 *Listeria monocytogenes*-Based Immunotherapy

Listeria monocytogenes (*Lm*) is an attractive platform for presentation of tumor-associated antigens and activation of immune response directed against cancer cells. *Lm* provides both a

potent stimulation of innate immunity and also induces an adaptive immune response through recruitment and activation of CD4⁺ and CD8⁺ T-cells specific for encoded heterologous antigens (Bahjat, 2006; Portnoy, 2002; Shen, 1995; Slifka, 1996). Repeat dosing with *Lm* is feasible; previously existing anti-*Lm* immunity did not affect generation of a T cell response to a *Lm*-expressed antigen, nor reduce resulting therapeutic efficacy in a mouse B16 melanoma model system (Starks, 2004).

In wild-type form, *Lm* is a bacterium commonly found in soil and water, and may be present in a variety of raw and processed foods. Listeriosis is a foodborne illness caused by wild-type *Lm* which primarily affects pregnant women and immunocompromised individuals. To address this safety concern a live, attenuated, double-deleted *Lm* (LADD) based immunotherapy platform was developed (ANZ-100). ANZ-100 has deletions of 2 genes, *actA* and *inlB* (*Lm* Δ *actA*/ Δ *inlB*). These genes encode the virulence-determinant proteins ActA and Internalin B, two proteins that facilitate cell-to-cell spread and invasion of nonphagocytic cells, in particular hepatocytes (Brockstedt, 2004). The deletions limit growth in the liver, a principal target organ of infection by wild-type *Lm*, by blocking direct hepatocyte infection via the InlB-hepatocyte growth factor receptor interaction and ActA-mediated cell-to-cell spread into hepatocytes from infected liver-resident Kupffer cells (Dramsi, 1995; Portnoy, 2002). Uptake of ANZ-100 by macrophages and other phagocytic cells in the liver and spleen is retained and results in a local inflammatory response as well as activation and recruitment of natural killer cells and T cells to the liver. In mice, ANZ-100 retains the immunostimulatory potency of wild-type *Lm* but with 1000-fold attenuation of virulence (Brockstedt, 2004). In a Phase 1 dose-escalation study, ANZ-100 doses up to 3×10^8 colony-forming units (CFU) administered by intravenous (IV) infusion in adults with carcinoma and liver metastases were well-tolerated (Le, 2012).

4.1.2 CRS-207

[figure not shown]
Mesothelin is a tumor-associated antigen with limited expression on the surface of normal tissues, but highly expressed in many human tumors including virtually all mesothelioma (Hassan, 2004). Mesothelin is expressed in 44-50% of human gastric cancer; presence of luminal or membranous staining of mesothelin has been correlated with poor patient outcome (Einama, 2012; Illei, 2016). In esophageal adenocarcinoma, 29-46% of tumors stained positive for mesothelin; expression correlated with development of malignancy in cases of Barrett's esophagus (Alvarez, 2008; Rizk, 2012). These features make mesothelin an attractive target for active tumor-specific immunotherapy.

ANZ-100 was subsequently engineered to express mesothelin, resulting in CRS-207 (*Lm* Δ *actA*/ Δ *inlB*/hMeso). CRS-207 contains an expression cassette encoding human mesothelin integrated at the *inlB* locus. After uptake of CRS-207 by dendritic cells and macrophages, mesothelin is expressed and released into the cytosolic compartment and subsequently processed through the endogenous major histocompatibility complex (MHC) Class I presentation pathway, resulting in activation of mesothelin-specific cell-mediated immunity (Le, 2012). Other mechanisms to activate mesothelin-specific, cell-mediated immunity may include uptake and

cross-presentation of antigens by dendritic cells and other cells after infection by CRS-207 and apoptosis. CRS-207 is a LADD construct rendering it greater than 1000-times less toxic in mice than wild-type *Lm* (Brockstedt, 2004). Nonclinical and clinical data are available and support continued clinical development.

